#### **4.2 Exclusion Criteria**

1. Any concurrent active malignancy requiring treatment (other than basal or squamous cell carcinoma of the skin, carcinoma in situ of the cervix, superficial bladder tumors, or other malignancies curatively treated > 3 years prior to study entry)
2. History of severe cardiovascular disease within the last 12 months: symptomatic congestive heart failure, myocardial infarction, coronary artery disease (CAD), life threatening arrhythmias, uncontrolled hypertension
3. Renal failure requiring hemo- or peritoneal dialysis
4. Unstable systemic diseases or active uncontrolled infection
5. Known history of HIV infection
6. Clinically significant gastrointestinal bleeding within 30 days prior to study entry
7. Major surgery, open biopsy or significant traumatic injury within 4 weeks prior to study entry
8. Child's-Pugh Class C
9. Any malabsorption problem that, in the investigator's opinion, would prevent adequate absorption of the study drug
10. Presence of any other medical complications that in the investigator's opinion, suggests a survival of < 3 months
11. Substance abuse, or medical, psychological or social conditions that may interfere with the patient's participation in the study or evaluation of the study results
12. Patient inability to swallow oral medications
13. Any condition that is unstable or which could jeopardize the safety of the patient and his/her compliance in the study
14. Pregnant or breast-feeding patients
15. Being of reproductive potential and unable or unwilling to practice an effective contraceptive method

16. Lack of positive staining for RB-function on tumor biopsy.

## **5.0 Treatment Procedures**

Before subjects are entered into the study and any study-specific procedures are performed, he/she must personally sign and date consent form and an informed consent discussion must be conducted. All appropriate committees and the Jefferson Institutional Review Board (IRB), prior to enrollment of any subjects on this study, must approve the study protocol, informed consent form and all study-related materials. The patient will be asked to fast for 1 hour before and 2 hours after dosing.

## **Treatment Schedule**

Treatment will be divided into 28-day cycles. One cycle of treatment will consist of 21 days (3 weeks) of daily oral administration of 125 mg PD-0332991 followed by 7 days without treatment for a total of 28 days (4 weeks) per cycle. Subjects may continue to receive PD-332991 for additional cycles until disease progression, intolerability, death, failure to return for follow up, and/or withdraw of consent. Patients will be evaluated at each visit and treatment continued at the discretion the Investigator

## **5.1 Visit 1 – Pre-study Evaluation**

Prior to performing study related procedures, subjects will read, understand and sign informed consent. Investigator and medical staff involved will discuss PD-0332991 treatment with potential candidate for the study and obtain informed consent. Pre-study evaluations (other than biopsy) are to be obtained within 28 days prior to start of treatment. These will include:

1. MUGA scan or Echocardiogram if clinically indicated
2. Pulmonary Function Test if clinically indicated
3. CT scan of chest, abdomen, and pelvis
4. MRI of the liver
5. Biopsy if required to confirm diagnosis of HCC and assess RB-pathway status via immunohistochemistry (IHC). PD-0332991 is a highly selective inhibitor of CDK4/6 that is dependent on a functional RB-pathway to exert its anti-proliferative effects. It is inactive against RB-negative tumors. The complete RB-pathway consists of several families of proteins: CDKN(INK4A), D-type cyclins, cyclin-dependent protein kinases (CDK4, CDK6), RB-family proteins, and E2F transcription factors. In addition to RB protein status, overexpression of CDKN (p16INK4A) protein is associated with lack of sensitivity to PD-0332991. In vitro efficacy tests have suggested that Ki67 may be used as a biomarker of cell proliferation and indirectly correlate with sensitivity to PD-0332991. For the current study, IHC of liver biopsy tissue will be used to assess protein expression of RB, p16INK4A and Ki67, which will then be used to determine whether a patient is eligible for trial participation (i.e. likely to show sensitivity to PD-0332991).

The following pre-study evaluations are to be obtained within 14 days prior to start of treatment:

1. Complete history, physical exam including height and weight
2. Performance status, Child-Pugh status

3. Blood cell counts (CBC with differential, platelets) and comprehensive metabolic panel (albumin, alkaline phosphatase, total protein, BUN, creatinine, AST (SGOT), ALT (SGPT), total bilirubin, calcium, sodium, potassium, chloride, bicarbonate), lactate dehydrogenase (LDH), pregnancy test, and TSH, PT/PTT, INR
4. Concomitant medication review

### **5.2 Visit 2 – Study Initiation (Start of cycle 1)**

After the eligibility is confirmed, subject will be enrolled into the study. The following assessments should be completed before the study drug is dispensed on the first day of treatment:

1. Clinical assessment – including complete physical examination to history, weight, vital signs, signs/symptoms, and performance status
2. CBC, comprehensive metabolic panel, coagulation studies
3. Serum AFP
4. Concomitant medication review

### **5.3 Visit 3 – Toxicity Assessment**

Initial safety and tolerability of the study drug will be assessed after 2 weeks on PD-0332991. The evaluation will include:

1. Clinical assessment – including interval history, physical examination, weight, vital signs, signs/symptoms, and performance status.
2. Toxicity assessment. Adverse events will be graded using the National Cancer Institute (NCI) Common Toxicity Terminology Criteria for Adverse Events v 4.0 (CTCAE v 4.0).
3. Concomitant medication review
4. Blood cell counts (CBC with differential, platelets) and comprehensive chemistries (albumin, alkaline phosphatase, total protein, BUN, creatinine, AST (SGOT), ALT (SGPT), total bilirubin, calcium, sodium, potassium, chloride, bicarbonate), lactate dehydrogenase (LDH).

If subject experiences a Grade 3 or greater toxicity deemed related to study drug, PD-0332991 will be temporarily discontinued. After the resolution of toxicity to Grade 2 or less, PD-0332991 will be restarted at the initial dose. The study treatment will be continued until disease progression or unacceptable side effects (Grade 3 or greater). Subjects with unacceptable side effects (Grade 3 or greater) for a second time on PD-0332991 will be removed from the study. The only exception to this are: Grade 3 anorexia, nausea vomiting, stomatitis/mucositis or diarrhea that will lead to investigational product withdrawal only if not manageable despite maximum supportive care.

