If a subject is not able to tolerate the 75 mg dose, then treatment should be discontinued. If a dose reduction has been performed, the subject may be re-escalated by the treating physician provided toxicities have resolved to Grade 2.

**Table 8.3** outlines the procedures for dose modifications for bone marrow toxicity related to PD0332991.

Due to baseline coagulopathy and tendency to have bleeding events due to underlying liver disease, dose modifications should not be based on hemoglobin values. If a subject experiences bone marrow toxicity of both WBCs and platelets the recommended dose adjustment should be based on WBC count. It is recommended that standard of care be followed for administration of RBCs and platelets and for vitamin K in patients with ESLD.

**Table 8.3** Dose modifications/delays for bone marrow toxicity related to PD0332991

Grade of Event CTCAE v 4.03	Dose Interruption	Dose Modification for Remainder of Cycle.	Dose Modification for Subsequent Cycles
0-2	Treat on time	No change	No change
3-4	
 
• Delay until <math>\leq</math> Grade 2
 
• Administer 6 mg pegfilgrastim (Neulasta) subcut if WBC/ANC does not recover to <math>\leq</math> Grade 2 after 1 week dose interruption
 
	
 
• First episode: No change
 
• Second episode within cycle after co-administration with pegfilgrastim: Reduce 1 dose level
 
	
 
• Continue at dose level from previous cycle
 
• If serious drug-related myelosuppression occurs including: A. febrile neutropenia or B. sepsis with neutropenia, in previous cycle institute permanent dose reduction at -1 dose level
 
• If bone marrow toxicity recurs at <math>\geq</math> Grade 3 with leucocyte growth factor administration then
 

			institute permanent dose reduction at -1 dose level 
 
• If unable to resume PD-0332991 due to BM toxicity for an entire cycle, institute permanent dose reduction at -1 dose level
 
• If bone marrow toxicity remains at <math>\leq</math> Grade 2 for remainder of a previous cycle after administration of pegfilgrastim, then administer with subsequent cycles, 6 mg subcut on day 1 once per cycle
 

--	--	--	---

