### **9.13 Non-Hematological and Hematological Adverse Events**

Patients will be assessed clinically for toxicity prior to each dose using the National Cancer Institute (NCI) CTCAE Version 4. If patients experience Grade 3 or greater toxicity deemed related to study drug, PD-0332991 will be temporarily discontinued. After the resolution of toxicity to Grade 1 or less, PD-0332991 will be restarted at the initial dose. The study treatment will be continued until disease progression or unacceptable side effects (Grade 3 or greater). Patients with unacceptable side effects (Grade 3 or greater) for a second time on PD-0332991 will be removed from the study. The only exception to this are: Grade 3 anorexia, nausea vomiting, stomatitis/mucositis or diarrhea that will lead to investigational product withdrawal only if not manageable despite maximum supportive care. Throughout the study investigators may prescribe any concomitant medications or treatments necessary to provide adequate supportive care other than experimental or approved anti-tumor therapies. All concomitant medications must be recorded.

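### Sections 5.3, 9.13 and Table 8.3 give conflicting instructions on when to restart drug after a Grade 3 or greater toxicity and on what follows a second such event

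*Combined protocol and SAP*

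**What the plan says.** **Restart.** Section 5.3 holds drug for a related toxicity of Grade 3 or more, and then: "After the resolution of toxicity to Grade 2 or less, PD-0332991 will be restarted at the initial dose". Section 5.4 carries the Visit 3 procedures forward to later visits, so 5.3 is not confined to week 2. Section 9.13, whose heading names both hematological and non-hematological events, says: "After the resolution of toxicity to Grade 1 or less, PD-0332991 will be restarted at the initial dose".

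**Second event.** Section 5.3: "Subjects with unacceptable side effects (Grade 3 or greater) for a second time on PD-0332991 will be removed from the study". Section 9.13: "Patients with unacceptable side effects (Grade 3 or greater) for a second time on PD-0332991 will be removed from the study". Both sections then give the same closed list: "The only exception to this are: Grade 3 anorexia, nausea vomiting, stomatitis/mucositis or diarrhea". Those events lead to withdrawal only if supportive care fails.

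**Marrow events in Section 8.4.** For Grade 3-4 marrow toxicity, Table 8.3 delays drug until Grade 2 or less. A first episode leaves the dose unchanged for the rest of the cycle. For a repeat in the same cycle it says: "Second episode within cycle after co-administration with pegfilgrastim: Reduce 1 dose level". For later cycles the default is "Continue at dose level from previous cycle". Named situations trigger a permanent one-level reduction, among them recurrence at or above "Grade 3 with leucocyte growth factor administration". The text before the table stops treatment if 75 mg is not tolerated and rules out hemoglobin as a basis for dose modification.

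**Withdrawal in Section 5.6.** Item 3 lists unacceptable toxicity without a grade. Item 8 withdraws a subject who receives under half the required dose in two consecutive cycles.

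**The concern.** An investigator facing one event can reach opposite actions depending on the section opened. The same subject could restart at different blood counts. After a second marrow event the subject could be removed under one section or kept on drug under another.

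These rules are likely to be used. Section 1.2 names myelosuppression as the principal dose-limiting toxicity. Section 9.10 reports eleven dose-limiting toxicities in the phase I study (N=74), all neutropenia and/or thrombocytopenia. Section 8.4 expects some subjects to enter with low counts from liver disease or hypersplenism.

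There is also an effect on the analysis. Section 11.1 counts a subject only after two cycles and the week 8 assessment, and replaces those who are not evaluable. Whether a subject with an early second event is removed can therefore decide whether that subject is analysed.

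**Working it through.** The plan has no figure to reproduce here. The check sets the texts side by side and converts grades to counts.

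**1. The rules compared**

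| | 5.3 | 9.13 | Table 8.3 (marrow only) |
|---|---|---|---|
| Restart at | Grade 2 or less | Grade 1 or less | Grade 2 or less |
| Dose at restart | initial dose | initial dose | unchanged, or one level lower in named situations |
| Second Grade 3 or greater event | removal | removal | continue, at a reduced or unchanged dose |

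For non-marrow toxicity, 5.3 and 9.13 conflict directly and Table 8.3 has no bearing. For marrow toxicity, 9.13 stands alone against the other two.

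**2. Restart grade as counts** (lower bounds from Table 8.2, entry minimums from Section 4.1, all ×10⁹/L)

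| | Grade 2 floor | Grade 1 floor | Ratio | Entry minimum |
|---|---|---|---|---|
| ANC | 1.0 | 1.5 | 0.67 | 1.5 |
| Platelets | 50 | 75 | 0.67 | 75 |
| WBC | 2.0 | 3.0 | 0.67 | 4.0 |

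A subject who recovers to an ANC of 1.2, or to platelets of 60, is at Grade 2. Drug may restart under 5.3 and Table 8.3, but not under 9.13. For ANC and platelets the Grade 1 floor equals the entry minimum, so the sections disagree on whether drug may restart below entry counts. That contrast does not extend to WBC, where both floors lie below the entry minimum.

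**3. Second marrow event.** Under 5.3 and 9.13 the subject leaves, because marrow toxicity is not in the exception list. Under Table 8.3 a second episode in the same cycle after pegfilgrastim means one dose level down. A second event in a later cycle can fall under the default of keeping the previous cycle's dose, or under a permanent reduction if a named situation applies. A subject removed at the second event could not follow these steps.

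**4. Does other text settle it?**
- *Section 5.4* leaves to the investigator's judgment whether an event is severe enough for removal. It does not rank 5.3 and 9.13 against Table 8.3.
- *Section 5.6, item 3* gives no grade and no link to the other rules.
- *Section 5.6, item 8.* If the required dose is 125 mg × 21 = 2,625 mg per cycle, half is 1,312.5 mg. Full adherence gives 100 × 21 = 2,100 mg (80%) or 75 × 21 = 1,575 mg (60%). If the required dose means the reduced dose, full adherence is 100%. A dose reduction alone therefore never triggers item 8, though long interruptions can. On the first reading that takes, in each of two consecutive cycles, at most 10 doses at 125 mg (1,250 mg), 13 at 100 mg (1,300 mg) or 17 at 75 mg (1,275 mg).
- *End of Section 8.4* requires sponsor-investigator approval of dose adjustments. It does not say that this covers a restart at an unchanged dose or removal from study.
- *Section 9.10* sends the reader to Section 8.1 for hematologic interruption rules, but 8.1 holds general drug information.
- *Sections 5.3 and 9.13* do not cite Section 8.

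**5. Evaluability.** The Protocol Summary requires 19 evaluable subjects and caps accrual at 25, which leaves 25 − 19 = 6 places for replacements. Each removal before week 8 could use one.

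**The case against.** The case on the other side concerns the second event more than the restart grade, where the contradiction is plain.

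- *Table 8.3 is the specific rule.* Its title and introduction limit it to marrow toxicity, and a specific table is often read as overriding general text. That is reasonable, and the table's scope is indeed written. Its precedence is not, and the heading of 9.13 and the closed exception list point the other way.
- *Removal is a matter of judgment.* The sentence in 5.4 does soften the removal rule. But 5.3 and 9.13 equate unacceptable with Grade 3 or greater and state removal as a requirement, so the conflict remains.
- *Text is missing.* Part of Section 8.4, between Table 8.2 and the instruction to stop if 75 mg is not tolerated, was not available to this review. It could contain a statement of scope. This lowers certainty about the second event. It does not affect the restart conflict for non-marrow toxicity.
- *An unchanged dose after a second event is partly inferred.* This is correct to a degree. Removal against reduction is explicit. Removal against an unchanged dose follows from reading together the first-episode rule and the default for later cycles.
- *The dose wording conflicts less than it seems.* This stands in part. Table 8.3 also leaves the dose unchanged after a first episode, so the mismatch with restarting at the initial dose is confined to its named reductions.

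**Conclusion.** The concern holds and must be fixed, because following the plan as written produces contradictory safety actions. The conflict over restart grade is certain. For marrow counts it is a difference between floors of 1.0 and 1.5 for ANC, 50 and 75 for platelets, and 2.0 and 3.0 for WBC (×10⁹/L). For non-marrow toxicity it is one full grade.

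The conflict over a second marrow event is strong on the available text. It rests on the assumption that the unavailable part of Section 8.4 contains no precedence statement.

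How many subjects would be affected cannot be computed, since the documents give no rate of second Grade 3 or greater events. The effect on evaluability arises only if such an event falls before week 8.

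**What to change.** Amend Sections 5.3, 9.13 and 8.4 with Table 8.3 into one rule set, and have 5.4, 5.6 and 9.10 refer to it. The rule set should state:

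- whether 5.3 and 9.13 apply to marrow toxicity or defer to Table 8.3;
- one restart grade for each type of toxicity;
- one consequence of a second Grade 3 or greater event, and how the investigator's judgment in 5.4 and unacceptable toxicity in 5.6 relate to it;
- consistent wording on the dose at restart, and on whether the hemoglobin exemption in 8.4 also applies in 5.3 and 9.13;
- whether sponsor-investigator approval covers restart at an unchanged dose and removal.

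Correct the pointer to Section 8.1 in 9.10 at the same time. Which grade and which consequence to adopt is for the sponsor-investigator and the clinical team. The cost is amendment wording only, with no extra patients or procedures.

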### **5.4 Subsequent visits on study – Response and Toxicity Assessment**

Safety and tolerability of the study drug will be assessed every 2 weeks after the initiation of PD-0332991 for the first 3 cycles of treatment, and every 4 weeks thereafter. Procedures will be as described for Visit 3. Additionally, Serum AFP will be monitored every 4 weeks and imaging will occur every 8 weeks after initiation of therapy to determine response of the disease to treatment. Subjects will undergo tumor response assessment per modification of RECIST (Version 1.1) guidelines. Radiological assessments must include CT of the chest, abdomen and pelvis and MRI of the liver. Magnetic Resonance Imaging is the preferred study for imaging the liver and must include T1, T2/flair and diffusion weighted imaging. Studies will be obtained at

baseline and according to schedule of observations until disease progression, death, withdrawal of consent, end of study or start of a new treatment. Unscheduled imaging may be conducted at the discretion of the Investigator.

Adverse events are defined in section 9.0. The investigator is responsible for reviewing all laboratory and clinical data, determining clinical significance and assessment of adverse events. It will be left to the investigator's clinical judgment to determine whether an adverse event is related and of sufficient severity to require subject's removal from treatment or from the study. The subject may also withdraw voluntarily from treatment due to what he/she perceives as an intolerable adverse event. If this arises the subject will be observed with extra visits until symptoms cease or the condition becomes stable. Adverse events will be graded using the National Cancer Institute (NCI) Common Toxicity Terminology Criteria for Adverse Events v 4.0 (CTCAE v 4.0).

### **5.5 Follow-up Visits**

After disease progression or drug intolerance, subjects will be scheduled for follow-up assessment approximately 30 days after the last administration of protocol specific therapy. At this visit subjects will undergo clinical assessment including: interval history, limited physical examination, weight, vital signs, signs/symptoms, and performance status. AEs and concomitant meds will be obtained. Bloodwork including: CBC, comprehensive metabolic panel, AFP will be collected and recorded. Subjects will be followed every 3 months in clinic to collect information on their general health status and their liver cancer. This visit must include at a minimum interval history, physical exam, concomitant medications and toxicity assessment. If possible other treatments, outcomes and survival should be obtained.

### **5.6 Withdrawal of Subjects**

The following criteria will be used to withdraw subjects from the study:

1. Evidence of progressive disease, as defined by RECIST (Version 1.1) criteria.
2. If as judged by the investigator the subject would be best served by a change in therapy or that it is in the patient's best interest to come off study.
3. Unacceptable toxicity.
4. Subject withdrawal of consent.
5. Noncompliance with study medication or protocol-required evaluations and visits as determined by the investigator.
6. If there is a major protocol violation, or if requested by a regulatory agency.
7. Death of a subject.
8. If subject receives less than 50% of the protocol-required dose of PD-0332991 for 2 consecutive cycles, for any reason.

At the investigator's discretion, a subject may be continued on study drug for additional treatment cycles if he or she is deriving clinical benefit from PD-0332991 and interval imaging results demonstrate mild progression e.g. 25% increase in the sum of the longest diameter of target lesions rather than less than or equal to 20% used to define stable disease. If at the next interval imaging the subject shows further progression rather than disease stabilization, he/she

must be withdrawn from the study. The Principal Investigator must approve of the continuation on study.

### **5.7 Follow-up after Withdrawal from the Study**

Subjects will be followed after withdrawal from the study and scheduled for follow-up visits. Safety data after the last dose of treatment is given until toxicity has resolved. Survival information will be collected via phone or visit on a quarterly basis for each subject if subject not able to come for regular visits.

## **6.0 Evaluation of Response**

### **6.1 Definition of Progressive Disease**

Progression will be evaluated in this study using the new international criteria proposed by the Response Evaluation Criteria in Solid Tumors (RECIST) Committee. Changes in only the largest diameter (unidimensional measurement) of the tumor lesions are used in the RECIST criteria. Note: Lesions are either measurable or non-measurable using the criteria provided below.

